**Study operations support for remote visits:**

Tools and systems are provided by the Sponsor and are available to sites and subjects to support remote visits:

- A courier service has been engaged to ship investigational study drug and other study supplies to the subject (or designee).

- A standardized HIPAA/GDPR compliant telemedicine platform will be provided so that site personnel can participate in remote visits that are conducted in the subject's home (or designated location), utilizing Home Health Providers.
- A Home Health Provider (HHP) service has been employed.
- Medically qualified and trained HHP staff employed will visit the subject's home (or designated location) and will work with Site Staff (SS) to conduct each remote study visit from the privacy of the subject's home or designated location (such as a caregiver's home).
- During these remote visits, in coordination with Site Staff, the HHPs will use the Rater Station to facilitate collection of patient reported outcomes, will collect blood samples for safety labs and PK testing, will collect ECGs, and will measure the subject's vital signs.
- All data collected during the remote visits will be transferred to the Investigator and the study site via established processes (either electronically or on paper).

Data signifying where the visit was conducted (in clinic or remote), how the data were collected, and who collected data remotely will be recorded in subject source documents and in the clinical study database.

A Home Health Provider Delegation Log will be used to record the names of HHP professionals who assist Site Staff with the conduct of the remote visits. This separate delegation log will distinguish between those individuals who are part of the site staff (recorded on Site Delegation Log) and those who are employed by the HH Provider.

#### **Logistics Arrangements for Remote Visits:**

For remote study visits, the home health personnel conducting the visit will be notified by the clinic-based study staff of each upcoming scheduled visit for the study subject(s). The clinic-based staff will coordinate with the home health personnel to ensure access to all necessary subject source documents, required equipment, and procedural instructions to complete the remote assessment.

Clinic-based staff will participate in the remote study visit(s) via the established telemedicine platform available for the study.

Home health personnel will transfer the source documents completed during the remote visit to the Investigator's site via established processes. Home health personnel will transfer via established secure means the data collected in electronic format to the appropriate data repository for inclusion in the clinical database.

Data collected in paper format (subject diaries and any handwritten source notes) will be retrieved by HHP during the remote visit and will be returned to the Investigator's site.

Appropriate technical support and training will be provided to facilitate remote conduct of required study assessments.

Laboratory samples collected by home health personnel during the remote visit will be prepared for shipment to designated laboratories following established collection and shipping procedures.

**Summary:**

In closing, the tools, mechanisms, and processes put into place as part of the Decentralized Platform support sites and subjects who choose remote visits. Further, they protect subject safety, privacy, and consistency in data collection and reporting. In the event of future resurgences of the COVID-19 pandemic, these tools, mechanisms, and processes will be available to sites and subjects who have selected the in clinic visit modality.

1. LIST OF ABBREVIATIONS

Table 1: List of Abbreviations

Abbreviation	Term
AE	adverse event
ALT	alanine aminotransferase
ANCOVA	analysis of covariance
BMI	body mass index
CMH	Cochran-Mantel-Haenszel
CRF	case report form
CSR	clinical study report
DOB	date of birth
dy	days
FAS	full analysis set
GCP	Good Clinical Practice
IRB	Institutional Review Board
KM	Kaplan-Meier
LLN	lower limit of normal
LS	least squares
MAR	missing at random
MedDRA	Medical Dictionary for Regulatory Activities
MI	multiple imputation
MMRM	mixed model repeated measures
mo	months
MSA	multiple system atrophy
NE	norepinephrine level
OTC	over-the-counter medication
PAF	pure autonomic failure
PD	Parkinson's disease
PP	per protocol
QTcF	corrected QT interval, Fridericia correction
RR	respiratory rate
SAE	serious adverse event

Abbreviation	Term
SAP	statistical analysis plan
SAS	Statistical Analysis System
SBP	systolic blood pressure
SD	standard deviation
ULN	upper limit of normal
VAS	visual analogue scale
WBC	white blood cell count
WHO	World Health Organization
yr	years

2. INTRODUCTION

This document describes the plan for the summarization and analysis of clinical data collected in Study 0169 for amprelosetine (TD-9855). It serves as the final authority regarding data analyses.

3. STUDY OBJECTIVES AND ENDPOINTS

3.1. Study Objectives

3.1.1. Primary Objective

The primary objective of the study is:

- To evaluate the efficacy of amprelosetine (TD-9855) in subjects with multiple system atrophy (MSA), Parkinson's disease (PD), or pure autonomic failure (PAF) experiencing symptomatic neurogenic orthostatic hypotension (nOH) compared with placebo at Week 4, as measured by the change from baseline of the Orthostatic Hypotension Symptom Assessment (OHSA) Question 1 (OHSA#1) score.

3.1.2. Secondary Objectives

The secondary objectives of the study are as follows:

- To evaluate the efficacy of amprelosetine (TD-9855) by symptom and activity assessments using OHSA and the Orthostatic Hypotension Daily Activities Scale (OHDAS).
- To evaluate the efficacy of amprelosetine (TD-9855) using the Patient Global Impression of Change (PGI-C).
- To evaluate the efficacy of amprelosetine (TD-9855) in preventing incidence of falls.
- To evaluate the safety and tolerability of amprelosetine (TD-9855), including adverse events (AEs) and changes in blood pressure (BP), heart rate (HR), electrocardiogram (ECG), Columbia Suicide Severity Rating Scale (C-SSRS) and laboratory tests.

3.1.3. Exploratory Objectives

[REDACTED]

[REDACTED]

[REDACTED]

[REDACTED]

3.2. Study Endpoints

3.2.1. Primary Study Endpoint

The primary study endpoint is:

- Change from baseline in OHSA#1 (dizziness, lightheadedness, feeling faint, or feeling like blacking out) at Week 4

3.2.2. Secondary Study Endpoints

- Change from baseline in OHSA composite score in Weeks 1 to 4
- Change from baseline in OHDAS composite score in Weeks 1 to 4
- PGI-C at Week 4
- Incidence of falls

3.2.3. Exploratory Study Endpoints

[REDACTED]

[REDACTED]

3.2.4. Safety and Tolerability Endpoints

[figure not shown]
- Physical examination
- Neurological examination
- Vital signs including ambulatory BP
- Resting ECGs
- Clinical laboratory tests, including biochemistry, hematology, urinalysis
- Concomitant medication
- AEs
- Subject compliance to study treatment
- C-SSRS

4. STUDY DESIGN

4.1. Summary of Study Design

This is a Phase 3, randomized, double-blind, placebo-controlled, parallel-group, multicenter study to evaluate efficacy, safety, and tolerability of ampreloxetine (TD-9855) in subjects with primary autonomic failures (MSA, PD, or PAF) and symptomatic neurogenic orthostatic hypotension (nOH) after 4 weeks of treatment. Given the challenges presented by the COVID-19 pandemic the trial utilizes an operational design featuring the ability to conduct protocol required visits as either in clinic or remote visits. Investigators must conduct all study visits for Study 0169 for a given subject in a consistent manner for each subject to reduce the possibility of variability in data collection and reporting. Therefore, Investigators, in discussion with each individual subject at their site, will be required to elect to conduct all visits either in the clinic or remotely for each individual subject at their site. Regardless of which election an Investigator and subject make, the Screening visit (V1) must be conducted in clinic for all subjects. Tools and systems are available to sites and subjects to support remote visits (e.g., direct to subject shipping of study medication and other study supplies, standardized HIPAA/GDPR compliant telemedicine platform, in-home health nurses).

These options apply to each Individual Subject at a Site as appropriate

Due to the potential for resurgence of COVID-19 and its impact on both sites and subjects, the Sponsor will allow Investigators to request exceptions to the selected type of study visit modality due to COVID-19 or COVID-19 related circumstances. Approved exceptions will be recorded as COVID-19 related protocol deviations.

[figure not shown]
All sites are allowed at Investigator discretion to conduct either in-clinic or remote unscheduled visit(s) for subject safety or unexpected subject medical needs outside of the regular visit schedule. In this case, unscheduled visits are not considered protocol deviations and the Investigator is not required to obtain preapproval from the Sponsor. Data collected during these visits may include any protocol-specified assessments which will be captured in the clinical database.

For subjects that have previously completed the Screening visit at the time regulatory and ethics approval for [REDACTED] is received, sites must re-consent the subject using the most recently approved version of the Informed Consent Form to obtain subject consent for remote study visits, if that visit modality is selected by the Investigator and the subject. For those subjects who are already randomized to study treatment and active in the study at the time regulatory and ethics approval for [REDACTED] is received, the Investigator and subject should continue the remaining study visits in the same visit modality as the Randomization Visit.

Symptomatic neurogenic orthostatic hypotension is defined as:

- A sustained reduction of BP of ≥ 20 mm Hg (systolic) or ≥ 10 mm Hg (diastolic) within 3 minutes of standing or tilted-up to $\geq 60^\circ$ elevation from a supine position.
- A score of at least a 4 on the Orthostatic Hypotension Symptom Assessment Question #1

The study consists of 3 periods: (i) 4-week screening, (ii) 4-week randomized treatment, and (iii) 2-week follow up. The schematic representation is as shown below:

After signing the informed consent, the subject will enter a screening period of up to 4 weeks to confirm eligibility. At the screening visit, which must be performed in the clinic for all subjects, the subject will provide a comprehensive medical history of their disease and treatments. The subject's disease will be characterized and documented by the investigator.

The subject will receive an assessment of their physical condition, including safety and laboratory evaluations and related aspects of their disease states according to the Schedule of Study Procedures (Table 2). The presence of nOH symptoms and reported sensation of dizziness, lightheadedness, feeling faint, or feeling like blacking out (OHS#1) must be confirmed by the application of a tilt-table test. This tilt-table test serves 2 purposes: (i) determination of the systolic/diastolic BP changes, and (ii) training the subjects to recognize the sensations associated with OHS#1.

Eligible subjects will undergo training of accurate scoring of their sensation of dizziness, lightheadedness, feeling faint, or feeling like blacking out as outlined by the OHS#1.

Following the screening period, the subject will proceed to Visit 2 to further confirm the additional eligibility criteria prior to randomization. This includes the completion of the Orthostatic Hypotension Questionnaire (OHQ) in which a minimum score of 4 points in OHS#1 is required. Subjects meeting all applicable inclusion criteria and none of the applicable exclusion criteria, including confirmation of relevant criteria by the independent Enrollment Steering Committee (ESC), will be randomized to receive either amprelosetine (TD-9855) or matching placebo for the next 4 weeks.

Following randomization and completion of study assessments, the subject will receive a [REDACTED] of amprelosetine (TD-9855) (or matching placebo) [REDACTED] for the remaining double-blind treatment period.

Subjects completing the 4-week double-blind treatment period will be eligible to enroll and continue receiving study medication in Study 0170. The final visit for those subjects who do not complete the 4-week double-blind treatment period or who choose not to continue into Study 0170 will be the follow-up visit (V7). This visit must be completed two weeks from the date of the last dose.

The subject will return for weekly assessments as outlined in the Schedule of Study Procedures (Table 2).

4.2. Definition of Study Drugs

Study drug includes the following (placebo and amprelosetine [TD-9855]):

- Amprelosetine (TD-9855) [REDACTED]: Taken orally for 4 weeks without regard to food at approximately the same time each morning with approximately 8 ounces of water
- Placebo once daily: Taken orally for 4 weeks without regard to food at approximately the same time each morning with approximately 8 ounces of water

[REDACTED]

- [REDACTED]
- [REDACTED]
- [REDACTED]

4.3. Sample Size Considerations

[REDACTED]

[REDACTED]

[REDACTED]

4.4. Randomization

Central randomization for treatment allocation will be implemented. A computer-generated randomization schedule will be prepared for this study under the supervision of the sponsor.

Subjects will be randomized at Visit 2 in a 1:1 ratio to amprelosetine (TD-9855) or placebo using a randomization schedule stratified by disease type (MSA, PD, or PAF).

At least 40% of the subjects enrolled will have MSA (at least 76 subjects).

4.5. Clinical Assessments

Table 2: Schedule of Study Procedures

Study Period:	Screening	Treatment					Follow-up
Day (Visit):	Day -28 to -7 (Visit 1)	Day 1 (Visit 2)	Day 8 (Visit 3) +/- 3 days	Day 15 (Visit 4) +/- 3 days	Day 22 (Visit 5) +/- 3 days	Day 29 (Visit 6) / ET +/- 3 days	Day 43° (Visit 7) +/- 3 days
Mandated Order of Procedures (when applicable)							
Informed consent	X						
Inclusion /exclusion criteria	X	X					
Medical history (including smoking history)	X ^b						
Concomitant medications (and smoking usage)	X ^b	X	X	X	X	X	X
MoCA	X						
OHQ subject training ^c	X ^c	X	X	X	X	X	
OHQ (OHSA and OHDAS)		X ^m	X	X	X	X	
PGI-C						X	
C-SSRS	X	X ^{m,n}	X ⁿ	X ⁿ	X ⁿ	X ⁿ	X
Tilt-table test	X ^d						
Randomization		X ^a					
Recommended Order of Procedures (when applicable)							
██████		██				██	
██████		██				██	

Study Period:	Screening	Treatment					Follow-up
Day (Visit):	Day -28 to -7 (Visit 1)	Day 1 (Visit 2)	Day 8 (Visit 3) +/- 3 days	Day 15 (Visit 4) +/- 3 days	Day 22 (Visit 5) +/- 3 days	Day 29 (Visit 6) / ET +/- 3 days	Day 43° (Visit 7) +/- 3 days
████████████████████		█				█	
████████████████████		█				█	
████████████████████		█				█	
████████████████████		█				█	
██████████		█				█	
██████		█	█	█	█	█	
████████████████████	█	█	█	█	█	█	
Vital Signs (Body Temperature, Heart Rate, Respiration Rate, Blood Pressure) ^f	X	X ^m	X	X	X	X	X
Height (cm)	X						
Weight (kg)	X	X ^m	X	X	X	X	X
Physical examination	X	X ^m				X	
Neurological examination	X	X ^m				X	
12-lead electrocardiogram ^g	X					X	
Pregnancy test ^h	X	X ^m				X	
Norepinephrine (NE)	X						
Safety laboratory test (chemistry, hematology, and urinalysis)	X	X ^m		X		X	
████████████████████			█	█		█	

Study Period:	Screening	Treatment					Follow-up	
		Day (Visit):	Day -28 to -7 (Visit 1)	Day 1 (Visit 2)	Day 8 (Visit 3) +/- 3 days	Day 15 (Visit 4) +/- 3 days		Day 22 (Visit 5) +/- 3 days
ESC (for confirmation of diagnosis) ^a	X							
24-hour ambulatory BP device provision ^k	X	X		X				
24-hour ambulatory BP device collection ^k		X	X		X			
Incidence of Falls and ABPM position Diaries	X	X ^m	X	X	X	X		
Dosing and Midodrine rescue medication Diaries		X ^m	X	X	X	X		
Adverse events	X	X	X	X	X	X	X	
Dispense study medication		X ^m						
Study medication dosing ^l			X					
Collect, review, and re-dispense study medication			X	X	X			
Collect and review study medication						X		
Valsalva maneuver	X ^q							

Abbreviations: [REDACTED]; BP: Blood Pressure; [REDACTED]; C-SSRS: Columbia Suicide Severity Rating Scale; ESC: Enrollment Steering Committee; ET: Early Terminated; [REDACTED]; HR: Heart Rate; MoCA: Montreal Cognitive Assessment; [REDACTED]; OHDAS: Orthostatic Hypotension Daily Activity Scale; OHSA: Orthostatic Hypotension Symptom Assessment; OHQ: Orthostatic Hypotension Questionnaire; [REDACTED]; PGI-C: Patient Global Impression of Change; Randomization and trial supply management (RTSM); RR: Respiratory Rate; [REDACTED]

- a. [REDACTED] d in clinic for ALL subjects. Subject eligibility will be assessed by the Investigator during Screening and primary diagnosis will be verified by the ESC prior to randomization; subjects meeting OHSA#1 criterion on Visit 2 (Day 1) and who otherwise meet eligibility criteria may be randomized via RTSM.
- b. A complete medical and medication history evaluation will be performed during screening.
- c. During the screening visit, subjects will receive thorough training on the OHQ disease instrument and will receive refresher training prior to completing the OHQ during each study visit (Visit 2 to 6). Subjects should be rested prior to beginning the training.
- d. During Screening, the tilt-table test should be performed following at least 12-hours of withdrawal from vasoactive medications. The tilt-table test should be performed at least 2 hours after meals and with an empty bladder.
- e. The UPDRS scale should be completed in an ON state, and within 1-4 hours of taking the PD medications. All 6 parts would be completed on Day 1, while only Parts 2 and 3 of the questionnaire would be completed on Day 29.
- f. The vital sign measurements should be performed after the subject has rested sufficiently as determined by the appropriate site staff. The BP and HR collected at 10 minutes supine and seated from the orthostatic standing test can be used for safety vital signs assessment. Vitals can be performed as part of the mandated procedures, if needed.
- g. ECGs are done in triplicate after the subject has been resting for at least 5 minutes in a seated or supine position before the first reading, with each replicate separated by at least 1 minute.
- h. In women of childbearing potential only. First, urine beta human chorionic gonadotropin (bHCG) test will be performed and if positive, confirmation with serum bHCG test is required. The pregnancy test must be confirmed negative for a subject to be eligible for this study.
- i. [REDACTED]
- k. Ambulatory blood pressure monitoring equipment will be provided to the subject during the screening visit. Beginning approximately 72 to 24-hours before a subject conducts the Day 1 (Visit 2), and before the Day 8 and Day 22 visits, subjects will put on the 24-hour blood pressure monitoring equipment and initiate the recording. Once the 24-hour session is complete, subjects will remove and return the equipment to the research center during the next visit. During each 24-hour session, the blood pressure monitoring device will be programmed to automatically measure blood pressure every 2 hours beginning at the top of the hour. During each 24-hour session, subjects should also maintain a log of their posture at the time of each blood pressure measurement. Details regarding the ambulatory monitoring will be provided in a separate manual.
- l. Study medication will be ingested in the morning at approximately the same time of day with 8 ounces of water. The exact time and day of dosing will be recorded on the mornings of study visits. Subjects should be reminded to maintain an adequate fluid intake during their scheduled visits.
- m. The assessments or procedures will be performed within 24-hours prior to subject taking the study medication (pre-dose). Following randomization and completion of study assessments, the subject will begin taking study medication on Day 2 in the morning.
- n. C-SSRS is to be completed following OHQ questionnaire from Visit 2 to Visit 6.
- o. Follow-up visit is only applicable for those subjects that do not proceed to Study 0170 and will be completed two weeks from the date of the last dose.
- p. The assessment should be performed at approximately (± 2 hour) the same time of day on Day 1 (except Screening). Subjects should abstain from eating for at least 90mins prior to this assessment.
- q. Valsalva maneuver is to be performed for PAF subjects only if no results are available within 24 months from the date of randomization.

5. TIMING OF PLANNED ANALYSES

The analyses will occur when all subjects have completed or terminated early from the study and the database has been cleaned and locked.

6. CONSIDERATIONS FOR DATA ANALYSES AND HANDLING

Analyses and tabulations will generally be prepared using [REDACTED]

Summary tables and listings will be prepared according to ICH Guideline E3 and include a “footer” providing explanatory notes.

6.1. Analysis Sets

6.1.1. Screen Failures

Subjects who give written informed consent but are not randomized are considered screen failures. Screen failure subjects and the reason for screen failure are captured in the EDC.

6.1.2. Randomized Analysis Set

The randomized analysis set comprises all subjects who are randomized.

6.1.3. Safety Analysis Set

The safety analysis set comprises all randomized subjects who receive at least 1 dose of study medication. The safety analysis set will be the analysis set for both general (baseline, exposure, and compliance) and safety analyses. Subjects in the safety analysis set will be grouped according to the study treatments they receive.

6.1.4. Full Analysis Set (FAS)

The Full analysis set (FAS) is defined as all randomized subjects who have received at least 1 dose of study medication and have baseline and at least 1 post baseline measurement of OHSA#1. The FAS is the primary analysis set for efficacy endpoints. FAS analyses will use the randomized treatments.

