#### 6.4.6.7. Incidence of Falls – Subject Diary

Falls in subjects with symptomatic neurogenic orthostatic hypotension are common and potentially catastrophic. They can lead to serious injuries including hip fractures or head trauma; furthermore, fear of falling can limit mobility and physical activity. Thus, incidence of subject-reported falls is being captured in a diary. Assessments will be performed as specified in the Schedule of Study Procedures (Table 1). An example of the instrument is provided in [Appendix 3](#).

[REDACTED]

[REDACTED]

[REDACTED]

[REDACTED]

[REDACTED]

[REDACTED]

[REDACTED]

[REDACTED]

[REDACTED]

**6.4.9.** [REDACTED]

[REDACTED]

[REDACTED]

[REDACTED]

[REDACTED]

[REDACTED]

[REDACTED]

[REDACTED]

[REDACTED]

[REDACTED]

[REDACTED]

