### 6.8.2. Subject Discontinuation

Any subject (or his or her legally authorized representative) may withdraw their consent to participate in the study at any time without prejudice. The Investigator must withdraw from the study any subject who requests to be withdrawn. A subject's participation in the study may be discontinued at any time at the discretion of the Investigator and in accordance with his or her clinical judgment. When possible, the tests and evaluations listed for the termination visit should be completed. If a subject withdraws before completing the study, the reason for withdrawal is to be documented on the CRF.

The sponsor will be notified of all subject withdrawals.

Reasons for which the Investigator may withdraw a subject from the study or a subject may choose to terminate participation before completion of the study include, but are not limited to, the following:

- Adverse Event
- Physician Decision
- Pregnancy
- Protocol Violation
- Withdrawal by Subject
- Other

The subject may also discontinue from the study if the study is discontinued by the Sponsor.

Subjects who discontinue study medication early because of an adverse reaction should be encouraged to continue their participation in the follow-up safety assessments. If a subject fails to return for scheduled visits, a documented effort must be made to determine the reason.

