8. EFFICACY

8.1. General Considerations

For all efficacy data analyses, the FAS will be used unless otherwise specified.

Nominal p-values (i.e., unadjusted for multiple testing) will be provided as appropriate.

If a statistically significant treatment effect on the primary efficacy endpoint has been demonstrated, secondary efficacy endpoints will be tested in a hierarchical fashion using 2-sided tests at the 5% level of significance until a failure to reject the null hypothesis occurs.

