8.4.2. Analysis of PGI-C and Incidence of Falls

There are two binary secondary efficacy endpoints and their analyses are described below.

Patient Global Impression of Change (PGI-C)

PGI-C is a 5-point scale depicting the overall change in a patient’s neurogenic orthostatic hypotension symptoms since the initiation of study medication. Patients rate their change as “Much better,” “A little better,” “No change,” “A little worse,” or “Much worse.” Early versions of the protocol (original and Amendment 1) used the PGI-C on a 7-point scale. For analysis purposes, the 7-point scale will be mapped to the 5-point scale (Table 4). However, the data will be listed as collected.

The PGI-C will be summarized as number and percentage of subjects with “better” and “no change or worse” at Week 4 (see Appendix 1).

The proportion of subjects with PGI-C responses indicating improvement and the proportion with at least one fall will be compared between treatment groups using a Cochran-Mantel-Haenszel chi-squared test stratified by disease type at baseline.

Table 4: Mapping of PGI-C From 7-Point Scale to 5-Point Scale

7-Point Scale	5-Point Scale
Very Much Improved	Much Better
Much Improved	
Minimally Improved	A Little Better
No Change	No Change
Minimally Worse	A Little Worse
Much Worse	Much Worse
Very Much Worse	

In case the treatment groups differ substantially with respect to timing of assessment, the PGI-C analysis will be supplemented by a sensitivity analysis restricted to subjects with PGI-C collected within the narrowed window study day 25 to 42.

A plot will be presented to show the CMH-weighted average proportion of subjects with PGI-C responses indicating improvement by treatment group at Week 4.

Incidence of falls

Incidence of falls will be summarized as number and percentage of subjects with at least one fall during the interval from the date of the first dose to the date of the last dose.

The falls analysis will be supplemented by corresponding analyses of the incidence of at least one near-fall and of the incidence of at least one fall or near-fall, and by generalized linear model-based analyses of the reported number of falls, near-falls, and falls or near-falls during the treatment period. For these count analyses, the null and alternative hypotheses will be

$$H_0: \theta = 1$$

$$H_1: \theta \neq 1$$

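### By default the gate-kept falls test runs on the FAS, so a dosed subject with no post-baseline OHSA#1 is left out even if a falls diary exists; an early injurious fall can itself cause that exclusion

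*SAP*

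**What the plan says.** - **Analysis set.** SAP 6.1.4 limits the FAS to randomised, dosed subjects who "have baseline and at least 1 post baseline measurement of OHSA#1", and adds: "The FAS is the primary analysis set for efficacy endpoints".
- **Default.** SAP 8.1: "For all efficacy data analyses, the FAS will be used unless otherwise specified".
- **Falls endpoint.** SAP 8.4.2 introduces PGI-C and falls with "There are two binary secondary efficacy endpoints and their analyses are described below". It counts "subjects with at least one fall during the interval from the date of the first dose to the date of the last dose", tests the proportion by Cochran-Mantel-Haenszel stratified by disease type, and adds near-fall and count analyses. It names no analysis set for any of these.
- **Status.** SAP 8.4.3 places falls fourth and last among the secondary endpoints tested at the two-sided 5% level.
- **Data source.** Protocol 6.4.6.7 and Appendix 3 take falls from a subject diary that is separate from the OHQ. Of falls, the protocol says: "They can lead to serious injuries including hip fractures or head trauma".
- **Early leavers.** Protocol 6.3.6 lists the OHQ at the early-termination visit, but Protocol 6.8.2 asks for that visit's assessments conditionally: "When possible, the tests and evaluations listed for the termination visit should be completed".

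**The concern.** A post-baseline OHSA#1 is needed to compute a change in OHSA#1. It is not needed to know whether someone fell. Carrying the FAS condition over to falls makes membership of the falls analysis depend on a different instrument, completed after randomisation.

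The condition is also not neutral with respect to the outcome. A subject who falls in the first days of dosing, is badly hurt and leaves the study is among those least likely to complete a later questionnaire. Such a subject leaves both the numerator and the denominator. If this happens more in one arm, the comparison is no longer between the groups as randomised, and a claim carrying error-rate protection rests on it. Losing early fallers mainly from placebo works against the drug; losing them mainly from active works in its favour.

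**Working it through.** **1. Which set applies.** SAP 8.4.2 treats falls as an efficacy endpoint and names no set, so the 8.1 default gives the FAS, and 6.1.4 then requires a post-baseline OHSA#1. The near-fall and count analyses follow the same route. No readable text makes an exception.

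**2. Who is lost.** The first scheduled post-baseline OHQ is Visit 3, Day 8 ± 3, so Day 5 to 11. The first dose is on Day 2, which SAP 6.3.1 calls study day 1, so this is study day 4 to 10. For an observed fall to be lost, all of the following must hold:
- the fall is dated between first and last dose;
- the subject has no OHQ at Visit 3 or any later visit, at early termination, or at an unscheduled visit;
- the falls diary nevertheless reaches the site.

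**3. Scale of the trial.** The total in the sample-size sections is redacted. SAP 4.4 gives at least 76 MSA subjects as 40%, so 76 / 0.40 = 190. As a check from Protocol 8.2 (difference 1.5, SD 3.0, two-sided 0.05, power 90%, 10% dropout):
- n per arm = 2 × (1.960 + 1.282)² × 3.0² / 1.5² = 84.1, rounded up to 85; total 170;
- 170 / 0.90 = 188.9, rounded up to 189, which agrees with about 190.

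With 1:1 allocation and everyone dosed (an assumption), this is 95 per arm. The planned 10% dropout is about 19 subjects over all reasons and all four weeks. Those who leave before any OHQ are some unknown part of them.

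**4. Sensitivity of the falls test (illustrative).** The documents give no fall rates and no early-exit rates, so all counts below are assumed. The test is an unstratified two-proportion test standing in for the stratified one: z = (a/n − b/m) / √[p̄(1 − p̄)(1/n + 1/m)]. For 33/95 active against 48/95 placebo, p̄ = 81/190 = 0.4263, the standard error is 0.0718, z = 0.1579 / 0.0718 = 2.20 and p = 0.028.

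| All dosed: active v placebo | p | Fallers removed | p after removal |
|---|---|---|---|
| 33/95 v 48/95 | 0.028 | 2 placebo | 0.041 |
| 33/95 v 48/95 | 0.028 | 3 placebo | 0.049 |
| 33/95 v 48/95 | 0.028 | 4 placebo | 0.060 |
| 33/95 v 48/95 | 0.028 | 1 to 4 from each arm | 0.027 to 0.023 |
| 33/95 v 48/95 | 0.028 | 1 active, 3 placebo | 0.040 |
| 34/95 v 48/95 | 0.040 | 2 placebo | 0.058 |
| 30/95 v 48/95 | 0.008 | 4 placebo | 0.020 |
| 35/95 v 48/95 | 0.057 | 1 active | 0.047 |
| 21/95 v 33/95 | 0.054 | 1 active | 0.039 |
| 10/95 v 19/95 | 0.069 | 1 active | 0.044 |

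The decision changes only where the starting p is near 0.05 and the removals are one-sided.

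**5. False-positive risk in the worst direction (illustrative).** Let both arms have the same true fall risk p, and let a share q of active subjects only fall and leave before any OHQ. The expected active rate in the FAS is (p − q)/(1 − q); for p = 0.20 and q = 0.03 this is 0.17/0.97 = 0.175. In 400,000 simulated trials per setting, with p of 20%, 35% or 50%, the chance of a false claim favouring active (nominal 0.025) was:
- q = 1%: 0.031 to 0.034;
- q = 3%: 0.042 to 0.062;
- q = 5%: 0.056 to 0.111.

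With all dosed subjects analysed it stayed at about 0.025. If such exits are balanced between arms, the bias largely cancels.

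**The case against.** **One questionnaire is enough.** Any OHSA#1 after baseline keeps the subject in: at Visit 3, at early termination, or at an unscheduled visit, which may include any protocol assessment. Home visits make completion easier. This stands, and it is why the number lost is probably small.

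**The diary may be missing too.** The diary is returned at visits, and for remote visits the home health staff collect it. At Visits 3 to 6 the OHQ comes in the block that must be done first, before diary review. A subject with no OHQ has therefore probably had no completed post-baseline visit. A reader might infer that observed falls would be discarded in appreciable numbers; the documents do not support that. The clear case, diary in hand and no OHQ, is narrow.

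**The examples are constructed.** This also stands. A reader might infer from the table that two to four subjects would decide the test, or that the rule favours the drug. Neither follows: rates, starting p-values and one-sided exits are all assumed, and the documents say nothing on how such exits would split between arms.

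**Limited reach.** Falls is tested only if the primary and three earlier secondary endpoints all succeed, and a fall reported as an adverse event stays in the safety tables. Both are true, but safety tables do not repair the gate-kept test.

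**Redaction.** Protocol 8.3 and 8.7 and SAP Appendix 1 are blacked out, so an exception there cannot be ruled out. The SAP's own FAS definition and default are readable, however, and SAP section 2 makes the SAP the final authority on analyses.

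**Conclusion.** The point holds as a rule that should be changed, not as a demonstrated bias. On the readable text, the falls test and its supporting analyses condition a diary outcome on a different post-randomisation questionnaire, and an early injurious fall can bring about the exclusion. The number affected is unknown, probably small and possibly zero, and the direction is unknown. The decision would change only if the falls result is borderline and such exits are imbalanced between arms. The primary endpoint and the OHSA and OHDAS endpoints are not touched.

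The numerical illustrations rest on 95 dosed per arm, assumed fall rates, exits in one arm only where a shift is shown, and an unstratified test. The finding itself rests only on SAP 6.1.4, 8.1, 8.4.2 and 8.4.3 read together.

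**What to change.** In SAP 8.4.2, before unblinding:
- State that the falls test and all fall and near-fall analyses use every randomised subject who took at least one dose, grouped by randomised treatment, whether or not a post-baseline OHSA#1 exists. Simply naming the safety set would not do, because SAP 6.1.3 groups that set by treatment received.
- Keep the diary as the event source in the main analysis. Taking events from adverse-event reports when the diary is missing would change how the gate-kept endpoint is ascertained.
- Keep the FAS version as supplementary.
- For dosed subjects with no returned diary, add sensitivity analyses: one counting reported fall adverse events, and a pair counting all such subjects first as fallers and then as non-fallers.

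No new data are needed. The cost is a short SAP amendment and a few extra tables. A few subjects with short exposure or a missing diary will enter the denominator, and the falls set will differ from that of the OHSA and OHDAS endpoints. The count models already allow for short exposure through their time-at-risk offset; the binary test does not, which is another reason to show the sensitivity analyses beside it.
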